1.5 Review of Literatures

YUECHONG CUI et al (2018) performed a systematic review and meta-analysis of RCTs that evaluated the effect of aspirin intake during pregnancy was performed. Relevant citations from January 1979 until October 2017 were extracted from the Embase, PubMed, Cochrane Central Register of Controlled Trials and Web of Science databases. All 10 RCTs evaluated the effect of low-dose aspirin for the prevention of preeclampsia irrespective of the time to delivery . As no heterogeneity was identified ($P=0.51$, $I^2=0\%$), the fixed-effects model was used for the meta-analysis. The results indicated that, compared with placebo or no treatment, low dose aspirin was associated with a 33% reduction in the relative risk of preeclampsia regardless of the time to delivery ($RR=0.68$, $95\% CI=0.57-0.80$; $P<0.0001$). Next, the efficacy in the two subgroups of preterm and term preeclampsia was evaluated . Analysis of the data from 6 RCTs indicated that low-dose aspirin, administered at ≤ 16 weeks of gestation, was associated with a 65% reduction in the risk of preterm preeclampsia. By contrast, no reduction in the relative risk of term preeclampsia by administration of low-dose aspirin was obtained ($RR=1.01$; $95\% CI=0.60-1.70$). (YUECHONG CUI et al .2018).

Rolnik, D.L.,et al (2017) conducted multicenter, double-blind, placebo-controlled trial among women with singleton pregnancies who were at high risk for preterm preeclampsia. 798 participants in the aspirin group and 822 in the placebo group. Preterm preeclampsia occurred in 13 participants (1.6%) in the aspirin group, as compared with 35 (4.3%) in the placebo group (odds ratio in the aspirin group,0.38; 95% confidence interval, 0.20 to 0.74; $P = 0.004$). (Rolnik,D.L.,et al.2017).

Michael I. et al (2014) on behalf of the USPSTF considered 19 RCTs (12 good-quality) and 2 good-quality observational studies to evaluate maternal,perinatal, and developmental harms. Studies of low- or average-risk pregnant women were included with trials of women at increased risk. Eleven RCTs (23 332 women) reported on the

outcome of placental abruption (6 trials in women with increased preeclampsia risk and 5 trials in women with low/average risk). Pooled analyses showed no statistically significant increase in abruption associated with aspirin (RR, 1.17 [95% CI, 0.93 to 1.48]; I² =36.4%).Eighteen trials reported on the outcome of perinatal mortality (with 4 smaller studies reporting no events).Pooled analyses (n = 22 848) on perinatal mortality (RR,0.92 [95% CI, 0.76 to 1.11]; 14 studies; I² = 0%) suggested no harm from low-dose aspirin. Nine trials (6 in women at increased preeclampsia risk and 3 in women at low risk; 22 760 women in total) reported on the outcome of postpartum hemorrhage. There was no evidence of a treatment effect (RR, 1.02 [95% CI, 0.96 to 1.09]) No evidence demonstrated that low-dose aspirin affected blood loss. The pooled relative risk for intracranial hemorrhage in neonates (6 studies; n = 22 158) was 0.84 (95% CI, 0.61 to 1.16), with low heterogeneity (I² = 27.1%; P = 0.23). Maternal death was a rare outcome and could not be evaluated.(Michael L. et al 2014).

Askie LM1 et al (2007) performed randomised trials of pre-eclampsia primary prevention. For women assigned to receive antiplatelet agents rather than control, the relative risk of developing pre-eclampsia was 0.90 (95% CI 0.84-0.97), of delivering before 34 weeks was 0.90 (0.83-0.98), and of having a pregnancy with a serious adverse outcome was 0.90 (0.85-0.96). Antiplatelet agents had no significant effect on the risk of death of the fetus or baby, having a small for gestational age infant, or bleeding events for either the women or their babies. (Askie LM1 et al (2007).

2. Materials and Methods

2.1 Study design

This will be a Randomized controlled trial.

2.2 Place of study

Department of Obstetrics & Gynaecology, BIRDEM-II General hospital, [name].

2.3 Study Period- one year

2.4 Study Population

Pregnant women with high risk for developing preeclampsia at gestational age 12 to 19 weeks will be divided into two groups-

Intervention (Patients with intake of aspirin) group:

Will be assigned to take 75mg aspirin after lunch in full stomach.

Control (Patients without intake of aspirin) group:

Will not assign to take aspirin.

3.5 Sampling technique

Simple randomization through lottery in a closed envelope. Randomization number will determine who will receive aspirin & who will not receive aspirin.

2.6 Study Procedure :

This Randomized clinical trial will be conducted in BIRDEM-II. Approval from Institutional Review Board will be taken. The study population will be pregnant women with risk factors for developing PE attending department of Obstetrics and Gynecology, BIRDEM-II. Pregnancy will be confirmed via USG. Then evaluation of risk factors of PE will be done by history taking, examinations & provided investigations. Those who will be eligible according to inclusion & exclusion criteria will be enrolled in the study. Trial information will be provided verbally & with a written information sheet. Participants will be randomized by lottery in a closed envelope, which will determine who receive aspirin daily & who will not. A total of 200 women will be included in the study, of whom 100 pregnant women having risk factors of developing pre-eclampsia will be in experimental group & another 100 pregnant women having risk factors for developing PE will be in control group. Experimental group will be prescribed to take 75 mg Aspirin daily after lunch from 12-19 weeks of pregnancy. Control group will not be prescribed to take Aspirin. For each and every subject separate data collection sheet will be prepared. Data will be collected from the patients using the structured design by history, clinical examination, urine & haematological investigations, USG of the patients. Both group of patients will get the usual advices & medications of pregnancy. All patients will be followed up at 19-24 weeks, 32-34 weeks of gestation, 36 weeks of gestation and weekly up to delivery. During follow up SBP & DBP will be carefully measured. Urine analysis will be done. Aspirin will be stopped either 36 weeks of pregnancy or when delivery occurs or when PE is diagnosed. Primary & Secondary outcome will be observed in both experimental & control group separately. Then analysis will be done by comparison of outcome of this two groups. Data will be analyzed using SPSS software.

2.7 Sample size determination:

Sample size is calculated using the following formula

$$n = \left[\frac{Z_{\alpha} \sqrt{p_1(1-p_1)} + Z_{\beta} \sqrt{p_2(1-p_2)}}{p_2 - p_1} \right]^2$$

Here, n= sample size

$p_1 = 1.6\%$ [Incidence of preeclampsia in experimental group (Rolnik et al., 2017)]

$p_2 = 8.71\%$ [Incidence of preeclampsia high risk group(Poon L.C et.al., 2019)]

$$p = \frac{p_1 + p_2}{2} = \frac{0.016 + 0.0871}{2} = 5.155\%$$

$Z_{\alpha} = 1.96$ at a 95% confidence interval

$Z_{\beta} = 0.84$ at a 80% power

Putting the values in the above equation the sample size n is estimates as

$$n = \left[\frac{1.96 \sqrt{0.016(1-0.016)} + 0.84 \sqrt{0.0871(1-0.0871)}}{0.0871 - 0.016} \right]^2 = 150.30 \approx 150$$

According to sample size determination it will be 150 in each group but 100 sample size in each group will be taken due to limitation of time.

2.8 Selection Criteria-Pregnant women have to fulfill any 1 of the following criteria to enroll the study

Inclusion criteria for both groups:

- Maternal age ≥ 18 years
- Advanced maternal age (≥ 35 years)
- BMI ≥ 30 kg/m²
- Live foetus at gestational age 12 weeks - 19 weeks.
- Pregnancy interval >10 years.
- Multiple pregnancy.
- Pregnancy assisted by Ovulation inducing drugs/ In vitro fertilization.
- Pregnant women with medical disorders-Chronic HTN,Hyperglycaemia in pregnancy,Thyroid disorder ,Autoimmune disease-APS,SLE.
- Previous history of Gestational HTN,PE, Eclampsia
- Previous history of IUGR, IUD, Still Birth.
- Family history of HTN, Gestational HTN, PE (mother and/or sister)

Exclusion criteria for both groups:

- Allergic to Aspirin.
- Peptic ulcer disease.
- Mental disease.
- Patient with treatment of antifolate drugs (antiepileptics, methotrexate)
- Patient who will not give consent to participate.

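### The sample size sets a preterm pre-eclampsia rate (1.6%) against a rate labelled pre-eclampsia (8.71%), so the 150 per group and 80% power are not supported for the primary outcome

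*Protocol*

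**What the plan says.** Section 2.7 plans for two rates at Z values of 1.96 and 0.84 (80% power):

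- p1 = 1.6%, labelled "Incidence of preeclampsia in experimental group" and attributed to a placebo-controlled aspirin trial.
- p2 = 8.71%, labelled "Incidence of preeclampsia high risk group" and attributed to an international guideline.

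It reports 150.30, rounded to 150 per group, and then says that 100 per group will be enrolled for lack of time.

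Section 1.5 describes the result of the same aspirin trial: "Preterm preeclampsia occurred in 13 participants (1.6%) in the aspirin group, as compared with 35 (4.3%) in the placebo group". It gives an odds ratio of 0.38 (95% CI 0.20 to 0.74) for that preterm outcome.

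The primary outcome in section 1.4 is the occurrence of pre-eclampsia. Section 2.10 defines it as new onset at or after 20 weeks, with no upper gestational limit, and section 2.6 follows women weekly from 36 weeks to delivery. Term cases therefore count.

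For pre-eclampsia at any gestation the protocol cites three effects:

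- Section 1.5, a meta-analysis of 10 trials: "low dose aspirin was associated with a 33% reduction in the relative risk of preeclampsia", with RR 0.68 (95% CI 0.57 to 0.80).
- Section 1.5, an individual-patient-data meta-analysis: RR 0.90 (0.84 to 0.97).
- Introduction, an earlier meta-analysis in high-risk women: a 19% reduction.

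The 10-trial review also gives a 65% reduction for preterm disease and RR 1.01 (0.60 to 1.70) for term disease.

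**The concern.** The two rates in the calculation do not describe the same outcome. The first counts only preterm disease. The second carries no such restriction in its label and comes from a different source. Part of the gap between them is therefore the difference between preterm and all pre-eclampsia, which aspirin does not produce. The calculation treats the whole gap as treatment effect.

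Section 1.3 states a directional efficacy hypothesis and section 2.13 tests at p<0.05, so the trial reads as confirmatory. If the planned effect is far larger than the evidence supports, a non-significant result will say very little but may be read as evidence against aspirin. A significant result will tend to overstate the benefit. A reader who sees only the admitted cut from 150 to 100 would think the shortfall much smaller than it is.

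**Working it through.** **1. The protocol's figure.** The standard pooled two-proportion formula, with p̄ = (0.016 + 0.0871)/2 = 0.05155, is

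n = [1.96·√(2p̄(1−p̄)) + 0.84·√(p1(1−p1) + p2(1−p2))]² / (p2−p1)²

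= (0.6129 + 0.2593)² / 0.0711² = 150.5 per group.

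This agrees with the stated 150.30. The formula actually printed in section 2.7 does not: (1.96·√(0.016·0.984) + 0.84·√(0.0871·0.9129))² / 0.0711² = (0.2459 + 0.2369)² / 0.0711² = 46.1.

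**2. Implied effect.** 0.016/0.0871 = 0.184, an 82% relative reduction. Within the cited trial, (13/798)/(35/822) = 0.38, for preterm disease. For any pre-eclampsia the cited values are 0.68, 0.90 and 1 − 0.19 = 0.81.

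**3. Power on the protocol's own rates.** For 1.6% v 8.71%, power is 80% at 150 per group and 62% at 100 by the normal approximation (84% and 64% by exact enumeration of the uncorrected chi-square test). The step from 80% to about 62–64% comes from the disclosed cut, not from the mismatch.

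**4. Power with the cited effects.** Exact two-sided chi-square power at 100 per group; the last column is the pooled formula at 80% power.

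| Scenario | Aspirin v control | Power, 100 per group | Per group for 80% |
|---|---|---|---|
| RR 0.68, any pre-eclampsia | 5.92% v 8.71% | 12% | about 1,370 |
| RR 0.57 (lower CI limit) | 4.96% v 8.71% | 18% | about 710 |
| RR 0.80 (upper CI limit) | 6.97% v 8.71% | 8% | about 3,740 |
| RR 0.81, any pre-eclampsia | 7.06% v 8.71% | 7% | about 4,160 |
| RR 0.90, any pre-eclampsia | 7.84% v 8.71% | 6% | about 15,700 |
| Preterm OR 0.38 carried over | 3.50% v 8.71% | 33% | about 330 |
| Preterm 65% reduction carried over | 3.05% v 8.71% | 39% | about 270 |
| Cited trial's own pair, preterm | 1.6% v 4.3% | 18% | about 615 (about 648 from the raw counts) |

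Restoring 150 per group raises the RR 0.68 row only to 15%.

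**5. Expected precision at RR 0.68.** Expected events are 5.92 and 8.71 per 100. SE(log RR) = √(1/5.92 + 1/8.71 − 2/100) = 0.51, so the 95% CI is about 0.25 to 1.86.

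**6. Sensitivity to the control rate.** This is an assumed range, since the documents give no other control rate for this population. With RR 0.68 and 100 per group, exact power is 18% at a 15% control rate, 23% at 20%, 29% at 25% and 34% at 30%.

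**The case against.** Four points on the other side have force.

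- **The control rate is uncertain.** Section 1.2 says most of this hospital's patients are diabetic and many are at high risk. Section 2.8 admits women with chronic hypertension, multiple pregnancy, autoimmune disease or previous pre-eclampsia. The true control rate may exceed 8.71%, and power would then be higher. This stands. A reader might infer that true power is 12% or less; the documents do not support that as a fact. Pairing assumed control rates of 15–25% with the lower CI limit of RR 0.57 gives 30–49%. That is better, but still well below 80%.
- **The shortfall is partly disclosed.** The protocol does not claim 80% power at 100 per group. This also stands, and the loss from 80% to about 62–64% belongs to the admitted cut.
- **A significant result need not be chance.** A reader might infer that it mostly would be. That share depends on a prior probability that no document gives. At RR 0.68, only 0.3 of the 11.6 percentage points of power lie in the wrong direction. What can be said is that a significant estimate would tend to be exaggerated.
- **Term disease.** A reader might take RR 1.01 to show that aspirin does nothing at term. Its interval of 0.60 to 1.70 does not show that. The point needs only that the 1.6% leaves term cases out and the primary outcome includes them.

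That a separate analysis plan may exist does not answer the point. The calculation is in the protocol, and its label contradicts the protocol's own review.

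**Conclusion.** The point holds. The 1.6% is mislabelled, the pair of rates mixes outcomes and sources, and the resulting RR of 0.18 is stronger than every effect the protocol cites, including those for preterm disease alone. The 150 per group and the 80% power are therefore not supported for any pre-eclampsia.

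With 8.71% in controls and 100 per group, power for the cited effects on any pre-eclampsia is about 6–12% (18% at the favourable limit of the RR 0.68 interval). Borrowing the preterm effects gives at most about 39%. All of this is conditional on 8.71%, whose meaning rests on the protocol's label alone. Over assumed control rates of 15–30% with RR 0.68 the range is about 18–34%. The exact size is uncertain, but power is inadequate under every one of these cases.

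**What to change.** In section 2.7:

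- Relabel the 1.6% as preterm pre-eclampsia.
- Base the calculation on an effect for any pre-eclampsia: RR 0.68, with 0.81 and 0.90 as sensitivity cases.
- State the power at 100 per group as conditional on the control rate, with the range shown above rather than a single figure.
- Print a formula that yields the stated result; the present one evaluates to about 46, not 150.30.

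In sections 1.3 and 2.13, present the trial as exploratory: report the RR with its 95% CI, and make no claim of no effect from a non-significant result.

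Recording gestational age at diagnosis is optional. The data sheet already holds LMP, EDD, dated visits with blood pressure and proteinuria, and weeks at delivery, so it can mostly be derived. On the cited preterm rates only about 2 v 4 events would be expected per 100 women.

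The cost is a change of wording and a much less favourable stated power. No extra patients are needed.

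### The sample-size equation printed in section 2.7 gives 46.1, not the stated 150.30; the target of about 150 per group is right for the stated inputs, but the displayed formula is not

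*Protocol*

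**What the plan says.** Section 2.7 (Sample size determination) opens with "Sample size is calculated using the following formula". The formula is n = [(Zα√(p1(1−p1)) + Zβ√(p2(1−p2)))/(p2−p1)]².

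The inputs are p1 = 1.6% for the aspirin group, p2 = 8.71% for a high-risk group, Zα = 1.96 and Zβ = 0.84, the last for 80% power. The section also averages the two rates to p = 5.155%. It then writes "Putting the values in the above equation the sample size n is estimates as", repeats the formula with the numbers in place, and gives 150.30, rounded to 150.

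The closing sentence says that "it will be 150 in each group but 100 sample size in each group will be taken due to limitation of time". The Methodology summary and section 2.6 (Study Procedure) likewise give 100 women in each arm, 200 in all.

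**The concern.** A sample-size calculation should return its stated answer when the stated inputs are put in. This one does not, and the gap is far too large for rounding.

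The form is also wrong for the design. Zα multiplies the standard deviation of one proportion and Zβ that of the other. That is the expression for testing one sample against a fixed reference rate. This trial compares two randomised groups, and section 2.13 plans a chi-square test between them, so sampling error in both groups has to enter both terms. The unused 5.155% suggests that a different formula was meant.

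At stake is whether the 80% power behind the target can be checked, and what power the trial has at the size it will enrol. The protocol gives no power for 100 per group, and a reader cannot obtain one from the equation as printed.

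**Working it through.** **Inputs, all from section 2.7.** p1 = 0.016; p2 = 0.0871; difference 0.0871 − 0.016 = 0.0711; mean p = (0.016 + 0.0871)/2 = 0.05155; Zα = 1.96; Zβ = 0.84; equal groups; no allowance for dropout.

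**Step 1: the equation as printed.**
- √(0.016 × 0.984) = √0.015744 = 0.1255; times 1.96 = 0.2459
- √(0.0871 × 0.9129) = √0.079514 = 0.2820; times 0.84 = 0.2369
- Sum 0.4828; divided by 0.0711 = 6.790; squared = **46.1**

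The stated 150.30 is not reproduced. Exchanging the p1 and p2 terms gives 85.7. Doubling gives 92.2 for the printed order and 171.3 for the exchanged order. None of these is near 150.30.

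**Step 2: the standard two-proportion formula with the mean p.**

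n = [Zα√(2p(1−p)) + Zβ√(p1(1−p1) + p2(1−p2))]² / (p2−p1)²
- √(2 × 0.05155 × 0.94845) = √0.097785 = 0.3127; times 1.96 = 0.6129
- √(0.015744 + 0.079514) = √0.095258 = 0.3086; times 0.84 = 0.2593
- Sum 0.8722; divided by 0.0711 = 12.267; squared = **150.47**, so 151 rounded up

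This is within 0.17 of the stated 150.30.

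**Step 3: other common formulas with the same inputs.**

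| Formula | n per group |
|---|---|
| Pooled (step 2) | 150.5 |
| Unpooled variance | 147.7 |
| Mean p in both terms | 151.7 |
| Arcsine | 131 |
| Pooled, continuity-corrected | 178 |
| Pooled, one-sided | 119 |

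The pooled two-sided formula comes closest to 150.30.

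**Step 4: power at the enrolled size, from the same formula.**

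z = [(p2−p1)√n − 0.6129] / 0.3086
- n = 150: (0.0711 × 12.247 − 0.6129)/0.3086 = 0.836; power about 80%
- n = 100: (0.0711 × 10 − 0.6129)/0.3086 = 0.318; power about **62%**

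**Step 5: the source of p1.** Section 2.7 attributes the 1.6% to a placebo-controlled trial that is summarised in section 1.5. There the figure is preterm preeclampsia in the aspirin arm (13 of 798, against 4.3% on placebo). In this protocol the primary outcome (section 1.4) is the occurrence of preeclampsia, and the definition in section 2.10 covers any onset at or after 20 weeks, with no preterm limit.

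**The case against.** The strongest reply is that only the display is at fault. About 150 per group is what the protocol's inputs require, and correcting the equation alters no enrolment, analysis or procedure. That stands, and it limits the point to an error of presentation in the calculation.

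A reader might go further and infer that 46 is the required size, so that 100 per group is more than double what is needed. The protocol does not support this: it prints 150.30 and 150 per group beside the equation, and 46 comes only from a formula that does not fit the design. A reader might also infer that the misprint conceals the reduction to 100. It does not. The next sentence of section 2.7 states the reduction and its reason, and the 100 comes from the time available, not from the equation. What is missing is the power that goes with it.

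Two smaller reservations remain. The text was read from PDF, so a misread equation cannot be wholly excluded; but the symbolic and numeric versions agree term by term, so the same loss would have had to occur twice. And the use of the pooled formula is inferred: it gives 150.47, not exactly 150.30. Rounding along the way probably explains the difference, and the otherwise unused 5.155% supports the inference without proving it.

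**Conclusion.** The point holds as an internal contradiction: the equation in section 2.7 yields 46.1, and the protocol reports 150.30. The reported target is essentially right for the stated rates, two-sided 5% significance and 80% power, and differs by one woman per group from the 151 obtained by rounding up.

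The practical consequence concerns the enrolled size. At 100 per group, under the protocol's own rates, power is about 62%. A non-significant result would therefore be weaker evidence against an effect than the 80% in section 2.7 suggests. This assumes equal groups, all 100 women in each group contributing to the analysis, and a chi-square test without continuity correction.

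Both the 151 and the 62% also depend on p1 = 1.6%. Preterm cases are a subset of all preeclampsia, so the all-gestation rate in that aspirin arm cannot be below 1.6% and may be higher. With p2 held at 8.71%, a higher p1 (still below p2) narrows the difference, raises the required number and lowers the power at 100. The corrected equation should therefore not be read as confirming 80% power for this trial's outcome.

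**What to change.** In section 2.7:

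1. Replace both displays of the equation with n = [Zα√(2p(1−p)) + Zβ√(p1(1−p1) + p2(1−p2))]² / (p2−p1)², using the p = 5.155% already given, and report 150.47, rounded up to 151 per group.
2. After the sentence on enrolling 100 per group, state that this gives about 62% power, not 80%, under the same rates.
3. Add that these figures rest on p1 = 1.6%, which section 1.5 reports for preterm preeclampsia, while the primary outcome here is preeclampsia at any gestation. If the sponsor has an all-gestation rate, rerun both figures with it.

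The cost is one equation and two or three sentences. Steps 1 and 2 require no change to design, enrolment or analysis.

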2.13 Data presentation and analysis plan

- Statistical analyses will be carried out by using Windows based Statistical Package for Social Sciences (SPSS-22.0).
- For continuous variables, distributions will be expressed by mean and standard deviation. Mean comparisons between two groups will be done by student's t-test.
- For qualitative variables, distributions will be expressed by frequency and their percentages. Chi square tests will be done to see the significance of differences between two groups.
- Relative Risk (RR) and 95% confidence interval will also be estimated for the outcome.
- The p value <0.05 will be declared as statistically significant.

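### Section 2.7 plans for 80% power with 150 women per group, enrols 100 instead and never restates the power, which is about 62% at its own rates

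*Protocol*

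**What the plan says.** Section 2.7 takes 1.6% as the preeclampsia rate with aspirin and 8.71% as the rate in high-risk women. It uses a normal deviate of 1.96 for a 95% interval and 0.84 for 80% power, and reports 150.30, rounded to 150 per group. Its closing sentence then says "it will be 150 in each group but 100 sample size in each group will be taken due to limitation of time". Section 2.6 fixes the same total: "A total of 200 women will be included in the study", split equally.

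Section 2.13 plans the analysis: "Chi square tests will be done to see the significance of differences between two groups". It adds a relative risk with 95% confidence interval, and "The p value <0.05 will be declared as statistically significant". Section 2.16 limits the analysis to women who complete the study according to protocol. No allowance for losses is given.

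Nowhere does the protocol give the power, or the detectable difference, for 100 per group.

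**The concern.** The one power figure in the protocol describes a trial of 300 women, and the trial to be run has 200. A reader who takes 80% from section 2.7 and 200 from section 2.6 will pair two numbers that do not belong together.

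What is at stake is how a non-significant result is read. Against a supposed 80% power it looks like moderately strong evidence that aspirin does not work in these women. Against the actual power it says little. Because section 2.13 judges results by a p-value threshold, the protocol should say in advance how much that threshold can detect with the women actually enrolled.

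**Working it through.** **Inputs.** From section 2.7: p1 = 0.016, p2 = 0.0871, difference d = 0.0711, z = 1.96 and 0.84, mean rate p = 0.05155. From sections 2.6 and 2.7: n = 100 per group. From section 2.13: chi-square test, p < 0.05.

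**1. Reproduce the 150.** The standard pooled two-proportion formula is

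n = [1.96·√(2p(1−p)) + 0.84·√(p1(1−p1) + p2(1−p2))]² / d²

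- √(2 × 0.05155 × 0.94845) = 0.3127; times 1.96 = 0.6129
- √(0.015744 + 0.079514) = 0.3086; times 0.84 = 0.2593
- n = (0.8722 / 0.0711)² = 150.5

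This matches the protocol's 150. The expression printed in section 2.7 does not. It has one group's variance under each root and leaves the mean rate unused:

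[(1.96 × 0.1255 + 0.84 × 0.2820) / 0.0711]² = 46.1

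So 150 is the right order of answer for these inputs, but the displayed formula and substitution do not produce it.

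**2. Power at 100 per group.** Invert the same pooled formula:

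z = (d·√n − 0.6129) / 0.3086 = (0.7110 − 0.6129) / 0.3086 = 0.318, so power = 62.5%

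| Women per group | Method | Power |
|---|---|---|
| 150 | Normal approximation | 79.8% |
| 150 | Exact, uncorrected chi-square | 84.0% |
| 100 | Normal approximation | 62.5% |
| 100 | Exact, uncorrected chi-square | 64.2% |
| 100 | Exact, Yates-corrected chi-square | 51.1% |

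Exact means summing the two binomial distributions over all tables that the test would declare significant.

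**3. Effect of losses.** The protocol gives no loss rate, so these are assumptions. With 5% not evaluable (95 per group) the normal approximation gives 60.2%; with 10% (90 per group) it gives 57.9%.

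**4. How far the 62% depends on p1.** The assumed rates imply a relative risk of 0.016 / 0.0871 = 0.18. The literature review in section 1.5 reports the 1.6% as the rate of preterm preeclampsia in the aspirin arm of a placebo-controlled trial. The outcome here (sections 1.4 and 2.9) is preeclampsia at any gestation. For preeclampsia regardless of time to delivery, section 1.5 cites a meta-analytic relative risk of 0.68. Applied to 8.71%, that gives 0.68 × 0.0871 = 5.92% on aspirin. The normal approximation then gives about 11% power at 100 per group and about 15% at 150.

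**The case against.** The strongest defence is that nothing is hidden. The 80% is an input to a calculation whose answer is 150, and the next statement says plainly that 100 will be taken and why. The protocol never asserts 80% power for 100 per group. That stands, and a reader who infers that it makes a false claim goes too far. What is missing is the power that follows from the smaller number, and without it the only figure on offer is the wrong one for this design.

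It could also be said that the printed formula yields 46.1, so 100 is ample. It does not help: that expression is not a valid two-group calculation, and the protocol itself concludes that 150 are needed.

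Two stronger readings are tempting.

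- A reader might infer that 100 per group reaches 80% power only if the aspirin rate is about 0.5% or lower. The normal approximation does give 0.47%, but it is poor when about half an event is expected in one arm. With the exact uncorrected chi-square test, power is 87% at 0.5% and reaches 80% at about 0.84%, a reduction of roughly 90% from 8.71%. With the Yates correction, power at 0.5% is 76%.
- A reader might infer that fewer than 100 per group will certainly be analysed, or that a null result will certainly be misread. The restriction to completers makes losses likely, but no rate is given, and no section plans to treat non-significance as proof of no effect. Both are risks, not facts in the document.

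Finally, the relative risk with its interval is already planned, so that part of a sound interpretation is in place. Rewording section 2.7 restores no power.

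**Conclusion.** The point holds as an unstated consequence of a disclosed cut. Moving from 150 to 100 per group lowers power from about 80% to about 62% at the protocol's own rates and two-sided 5% level, a loss of about 17 percentage points by the normal approximation (79.8% to 62.5%). The exact figure is 64% for the uncorrected chi-square and 51% with the Yates correction; the protocol does not say which version will be used.

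The 62% assumes that all 100 women per group are evaluable and that aspirin lowers the rate of any preeclampsia to 1.6%. The second assumption is optimistic, since section 1.5 reports that figure for preterm disease. Under the relative risk of 0.68 cited in the same section, power is about 11%, and the choice of p1 then matters more than the cut in numbers. The 62% should therefore be stated as conditional on the assumed rates, not as the trial's power without qualification.

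**What to change.** Replace the closing sentence of section 2.7 with:

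> Calculation gives 150 per group for 80% power; 100 per group will be enrolled because of limited time, which gives about 62% power for 1.6% vs 8.71% (about 58% if, as an assumption, 10% are not evaluable). A non-significant result will be reported as inconclusive, using the RR with 95% CI.

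Beside it, make two corrections to the same section:

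- Replace the printed formula and substitution with the pooled two-proportion formula, which gives 150.5; the expression now shown evaluates to 46.1.
- State that 1.6% is the rate cited for preterm preeclampsia while the outcome is any preeclampsia, so the 62% rests on an optimistic assumption. Give the figure of about 11% power at the cited relative risk of 0.68.

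The cost is protocol wording only. The stated power becomes less favourable. No outcome, test, visit or number of women changes, and the relative risk with 95% interval is already in section 2.13.
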